Appendix 1. Health questionnaire

Department for
Health

PreActiv digital prehabilitation project

HEALTH SCREENING QUESTIONNAIRE

Chief investigator: [name] [contact]

Researchers: [name] [contact]

[name] [contact]

[name] [contact]

It is important that volunteers participating in research studies are currently in good health to exercise. This is to ensure (i) their own continued well-being and (ii) to avoid the possibility of introducing bias into the study outcomes.

Please initial boxes:

1. Are you scheduled to have surgery in 10 weeks or more from today?

Yes No

2. Is the surgery you are scheduled for considered 'major surgery'? Please consult with your surgical team if you are unsure.

Yes No

3. Are you aged 50 years old or older?

Yes No

4. Are you able to understand written and spoken English, either independently, or with support from a family member or friend who can act as a translator throughout the study? Yes No

5. As far as you are aware, **do you suffer** or **have you ever** suffered from:

a) Any heart condition (e.g., heart attack, angina, arrhythmia, vessel disease, valve disease, heart failure, inflammation, aortic dissection, cardiomyopathy) Yes No

b) Blood pressure higher than 200/120 mmHg Yes No

c) Pulmonary embolism or infarct Yes No

d) Deep vein thrombosis Yes No

e) Stroke or transient ischaemic attack Yes No

f) Uncorrected medical conditions such as significant anaemia, important electrolyte imbalance, and hyperthyroidism Yes No

g) Mental or physical impairment limiting exercise Yes No

6. As far as you are aware, **do you suffer** from any of the following conditions:

a) Lung condition(s) Yes No

If yes, are your lung condition(s) well-controlled Yes No

b) Seizures Yes No

If yes, are your seizures well-controlled Yes No

c) Diabetes Yes No

If yes, is your diabetes well-controlled	Yes 	No 
d) Ongoing wound	Yes 	No 
If yes, could the wound be made worse by exercise	Yes 	No 
e) Ongoing infection	Yes 	No 
If yes, could the infection be made worse by exercise	Yes 	No 

7. Have you been hospitalised for a cardiovascular event within the past 12 months? Yes No

8. The Physical Activity Readiness Questionnaire (PAR-Q) is a standard questionnaire used to identify risks that require consideration when increasing physical activity level. Please answer the following questions to the best of your knowledge:

- a) Has your doctor ever said that you have a heart condition, and should only do physical activity recommended by a doctor? Yes No
- b) Do you feel pain in your chest when you do physical activity? Yes No
- c) In the past month, have you had chest pain when you were not doing physical activity? Yes No
- d) Do you lose your balance because of dizziness, or do you ever lose consciousness? Yes No

e) Do you have a bone or joint problem (for example back, knee or hip) that could be made worse by a change to your physical activity?

Yes No

f) Is your doctor currently prescribing drugs (for example water pills) for your blood pressure or heart condition? Yes No

g) Do you know of any other reason that you should not do physical activity?

Yes No

9. In the past week, did you perform:

a) Physical activities for a total of 2 hours and 30 minutes or more that made you breathe slightly harder than normal? Yes No

b) Physical activities for a total of 1 hour 15 minutes or more that made you breathe much harder than normal? Yes No

c) Muscle strengthening activities on two days or more? For example, lifting weights, using resistance bands, squats/push ups, heavy gardening

Yes No

10. PreActiv's digital prehabilitation is delivered via a website that can be accessed on a computer, laptop, smart-phone, or tablet. Do you have access to any of these technologies to access PreActiv's digital prehabilitation?

Yes No

11. Are you currently enrolled in any other research trials? Yes No

If you have answered **YES** to **questions 5-11**, please provide details below (e.g., to confirm the problem was/is short-lived, insignificant or well controlled).

Participant Name: _____

Participant Signature: _____

Date:

Participant ID:

Researcher Signature:

Date:

Thank you for your cooperation

Appendix 2. Feedback survey

Please tick one box per question that best represents your experience of PreActiv's prehabilitation

1 = Strongly agree, 2 = Agree, 3 = Unsure, 4 = Disagree, 5 = Strongly disagree

	1	2	3	4	5	N/A
Website						
It was easy to register on the website						
The website was user friendly						
I am satisfied with the website						
The website was easy to navigate						
Aesthetically the website looked good						
Exercise prescription						
The exercises in the programme felt appropriate for me						
The exercise videos were easy to follow						
The exercises were challenging						
The rating of perceived exertion scale (0-10) was easy to understand						
It was easy to complete the fitness test in the programme						
I felt motivated to follow the exercise videos						
I enjoyed doing exercises at home						
Booklet/eBook - 'A guide to prehabilitation'						
The booklet contained useful information						
I felt motivated to follow the guidance in the booklet						
I was happy to access the information as an eBook, instead of it being printed						
Support						

The community forum was a good source of support						
I received good tech support with using the platform (if required)						
I received good support from healthcare professionals through the platform						
Overall						
I would recommend the programme to a friend if they were having surgery						
I would continue to use the programme after the research ends						
I feel that the programme helped me to prepare for surgery						
Comments						
Please write any other comments or feedback here:						

The questions detailed above will be asked via PreActiv's website, to allow responses to be fully anonymised. An example screen displaying the questions is shown below:

My PreHub Feedback

Please rate how you found your prehabilitation programme by answering a few quick questions. Your responses are anonymous and will help us improve My PreHub for others.

STEP 1 OF 6

17%

About your experience with My PreHub

	Strongly Agree	Agree	Unsure	Disagree	Strongly Disagree
It was easy to register on the website					
The website was user friendly					
I am satisfied with the website					
The website was easy to navigate					
Aesthetically the website looked good					

Appendix 3. Baseline characteristics

Age (years)	Please write here:	
Please tick one		
Sex	Male	
	Female	
	Intersex	
Please tick one		
Ethnicity	White	
	Asian or Asian British	
	Black, Black British, Caribbean or African	
	Mixed or multiple ethnic groups	
	Other ethnic group	
Reason for surgery (diagnosis)	Please list:	
Surgery type	Please list:	
Medical conditions	Please list:	
Medications	Please list:	
Please write yes or no		
Mobility	Can you sit down and stand back up from a chair without pushing up on the arms of the chair, your legs, or a walking stick/frame?	

How do you typically travel to the RUH?	Please write (e.g., car, bus, taxi, walk, cycle etc):
How far is it from your home to the RUH?	Please give your best estimate of the total distance from home to the RUH and from the RUH back to home:
If you travel by car, please answer these questions	What is the year of your car? (e.g., 2013)
	What is the make of your car? (e.g., Ford):
	What is the model of your car? (e.g., Fiesta):
	What type of transmission does it have? (e.g., manual, automatic):
	What type of fuel does it use? (e.g., petrol, diesel, electric):
	Any further descriptions of the car? (e.g., engine size, turbo etc):

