- Retention (the proportion of patients that enrol into the study who complete follow-up measurements)
- Safety (the incidence and severity of adverse events)
- Acceptability (Likert scale and open-ended survey questions, posts in community forum)

The secondary aim is to assess the preliminary efficacy of PreActiv's digital prehabilitation by measuring pre- to post-intervention changes to:

- Cardiorespiratory fitness ($VO_{2\text{PEAK}}$, ventilatory threshold)
- Functional fitness (1-minute sit-to-stand test, 1-minute seated push-up test)
- Resting blood pressure and heart rate
- Self-reported physical activity level (International Physical Activity Questionnaire Short Form)
- Quality of life (EuroQoL EQ-5D-5L Scale)
- Mood (Hospital Anxiety and Depression Scale)

An exploratory aim is to evaluate the economic/environmental impact of PreActiv's digital prehabilitation:

- Cost per patient to deliver PreActiv's digital prehabilitation, with comparison to published costs for face-to-face and telemedicine prehabilitation programmes

- Environmental impact avoided by performing prehabilitation at home via PreActiv's digital prehabilitation compared to the estimated hypothetical emissions associated with participants travelling to the hospital three times per week for six weeks for face-to-face prehabilitation.

3. Study design

A single-arm pilot study conducted at the Royal United Hospitals Bath NHS Foundation Trust (RUH). All participants will be allocated to receive PreActiv's digital prehabilitation alongside usual care. Usual care at the RUH involves a digital preoperative assessment of surgical risk and relevant investigations such as electrocardiogram (ECG) and blood tests for all patients. For some patients, usual care may also include seeing an anaesthetist (depending on their risk factors) and seeing other allied healthcare professionals, e.g., dietician (depending on their individual requirements or the nature of the surgery). Prehabilitation is not standard of care at the RUH. Pre-intervention testing will be conducted in week 0 and post-intervention testing will be conducted in week 7.

4. Participant eligibility

The following inclusion criteria will define patients eligible for the study:

- Planned for major elective surgery ≥ 10 weeks from time of recruitment

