Based on these progression criteria, and aiming to test the hypothesis that feasibility outcomes will not fall within the red zone (*stop*) based on the expectation of being in the green zone (*go*) with 90% power and one-sided alpha of 0.05, we need to consent $N = 34$ participants. As such, recruitment will cease once $N = 34$ participants have provided written informed consent.

b. Recruitment, screening & informed consent

Participants will be recruited from the preoperative assessment clinic at the RUH. Preoperative assessment clinic is delivered predominantly via a virtual clinic ('MyPreOp') at the RUH, whereby patients complete questionnaires and provide consent for surgery online. However, all patients awaiting major elective surgery are required to attend the RUH for a blood test as a minimum, with patients aged ≥ 65 years and/or those with systemic disease also required to attend for ECG, as per the NICE guidelines (NICE, 2016). Preoperative nurses will identify potentially eligible patients who are booked for a blood test and/or ECG appointment according to study inclusion criteria. Preoperative nurses will email (emailing patients is part of normal practice) the participant information sheet to potentially eligible patients a minimum of 48 hours prior to their appointment. A short period between provision of study information and follow-up by the research team is justified in the context of potentially short surgical pathways in the study population.

During their appointment, the patient will be asked by the preoperative nurse if they are interested in participating in the study. If they are interested, the patient will be introduced to a researcher who will be present in the preoperative clinic. For those patients who are not interested in being involved in the study, we are interested in capturing the reasons why for research reporting and to inform the design of a future RCT. We will explain to these patients that they do not need to give a reason as they are free to decline to answer, but that it would be really helpful if they could explain their reason for declining involvement, as this will contribute to research reporting and future study design of this project.

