- Acceptability (week 7 only): collected via a survey integrated within PreActiv’s prehabilitation platform containing a combination of Likert scale and open-response questions about participant experiences of using PreActiv’s digital prehabilitation (Appendix 2). Responses to the survey will be fully anonymised, meaning responses cannot be attributed to the participant by name or study ID. Additional feedback will be obtained from comments submitted by participants to the community forum throughout the intervention.

Secondary outcome measurements will be conducted at the University of Bath during week 0 (pre-intervention) and week 7 (post-intervention), with each visit lasting 1-hour:

Participant characteristics

- Baseline characteristics (week 0 only): age, sex, ethnicity, surgery type, comorbidities, medications, mobility, transport to hospital visits (Appendix 3).

Physical assessments

- Resting blood pressure and heart rate will be measured using an automated sphygmomanometer after 15 minutes of seated rest.
- Cardiorespiratory fitness: Cardiopulmonary exercise tests (CPET) will be performed using a ramp-incremental protocol on a cycle ergometer. Body mass, height, and resting blood pressure will be measured prior to commencing exercise. After a 3-minute low-intensity warm-up, participants will be instructed to maintain a consistent cadence of 50-70 rpm during a ramp protocol whereby the resistance against the pedals increases incrementally over time. The rate of the incremental ramp protocol will range from 5-30 watts/minute, based on participant’s ability, with the aim of achieving maximal exertion within 8-12 minutes. Participants will be encouraged to exercise to maximal exertion. Heart rate, blood pressure, oxygen saturation, and rating of

perceived exertion (RPE) rated from 0-10 will be monitored throughout. A 5-minute low intensity cool-down will be completed after the ramp protocol with monitoring of heart rate and blood pressure recovery. Measurements of $VO_{2\text{PEAK}}$ and ventilatory threshold will be derived from CPETs.

- Functional fitness: 1-minute sit-to-stand test (for participants able to transition from seated to standing unsupported) or 1-minute seated push-up test (for participants unable, or requiring support, to transition from seated to standing).

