 - 1-minute testing protocols have been selected to increase the emphasis on measuring endurance rather than muscular strength, due to the associations between cardiorespiratory fitness and surgical outcomes. The 1-minute sit-to-stand test has been shown to induce similar cardiorespiratory responses as cardiopulmonary exercise testing in COPD patients (Gephine et al., 2020), and has been implemented in prehabilitation trials (Bradley et al., 2023). The 1-minute seated push-up test is a relatively novel assessment, and has been shown to correlate with other functional fitness measures (Chokphukiao et al., 2023, Poncumphak et al., 2023).
- Self-report physical activity: Participants will complete the IPAQ short-form questionnaire to self-report days per week and minutes per day of vigorous intensity physical activity, moderate intensity physical activity, walking, and sitting. 'MET-hours' (MET = metabolic equivalent of task) per week will be calculated. This information will be compared to the WHO guidelines on physical activity and sedentary behaviour.

Psychological assessments

- Quality of life: Participants will complete the EQ-5D-5L to provide insights into mobility, self-care, usual activities, pain/discomfort, and anxiety/depression.
- Mood: Participants will complete the Hospital Anxiety and Depression Score

Economic & environmental

- Cost per patient to deliver PreActiv's digital prehabilitation, with comparison to published costs for face-to-face and telemedicine prehabilitation programmes
- Environmental impact avoided by performing prehabilitation at home via PreActiv's digital prehabilitation compared to the estimated hypothetical emissions associated with participants travelling to the hospital three times per week for six weeks for face-to-face prehabilitation. Publicly-available carbon emissions data will be used for calculations.

e. Data analyses

The primary aim of this study is to test feasibility of the PreActiv's digital prehabilitation. Feasibility will be assessed by reporting proportions and comparing to predefined progression criteria (for adherence and retention). This pilot study is not adequately-powered to investigate the statistical significance of pre- to post-intervention changes to secondary outcome measures. As such, data analyses will be predominantly descriptive. Effect sizes will be reported to convey the magnitude of pre- to post-intervention changes to secondary outcomes.

6. Patient and public involvement (PPI)

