Participants will be provided with bespoke feedback on their test results after completing the study period. This will include physical activity level, blood pressure, cardiorespiratory fitness, and functional fitness, with reference to population norms and recommended guidelines – and highlighting any changes that occur between baseline and follow-up measures. Participants will also be awarded a certificate highlighting their progress throughout the digital prehabilitation intervention, including sessions performed and in-platform fitness test results.

Participants will receive free access to PreActiv's digital prehabilitation for six weeks [REDACTED]

Participants will be reimbursed for their travel costs associated with taking part in the study, including parking costs, and fuel costs paid at 45p per mile for study visits. Payments will be made via BACS transfer.

8. Risks of participating

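### The Appendix 3 distance item is labelled one way but prompts for a round trip, with no unit, so some answers may distort the exploratory avoided-emissions estimate

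*Combined protocol and SAP*

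**What the plan says.** Section 2 (Aims) introduces the outcome with the words "An exploratory aim is to evaluate the economic/environmental impact". Sections 2 and 5d define the environmental part as the emissions avoided by exercising at home, compared with "travelling to the hospital three times per week for six weeks for face-to-face prehabilitation". The protocol summary table lists environmental impact beside the secondary objective, but section 2 is explicit that it is exploratory.

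On method, section 5d says only: "Publicly-available carbon emissions data will be used for calculations". Section 5e (Data analyses) gives no formula for the emissions calculation.

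The participant-level distance comes from Appendix 3 (Baseline characteristics), collected in week 0 only. The left-hand cell asks "How far is it from your home to the RUH". The answer space beside it says "Please give your best estimate of the total distance from home to the RUH and from the RUH back to home". No unit appears in either cell. The rows around it ask for the mode of travel and, for car users, for year, make, model, transmission, fuel and any further description.

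**The concern.** The label and the prompt ask for two different quantities, one of them twice the other. The label is a complete question that can be answered as it stands, so a participant who reads it and skims the prompt may write a one-way figure. A bare number on the form would not show which question was answered, or whether it is in miles or kilometres.

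This is the only participant-level distance that the documents describe for the emissions calculation, and it enters as a multiplier. An error in it passes to that participant's result in full proportion, however carefully the car details are used to choose an emission factor. No section says whether the recorded distance will be doubled, or describes a check against an independent source. At stake is the accuracy of a figure that the protocol undertakes to report, and of an item that might be carried into the planned larger study.

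**Working it through.** The plan states no distance or emissions figure, so there is nothing to reproduce. The check is how a misread answer carries through.

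**Inputs**
- Journeys: three per week for six weeks (sections 2 and 5d), so 3 × 6 = 18 round trips per participant. With all 34 planned participants (section 5a) this is 18 × 34 = 612 round trips.
- Distance: the Appendix 3 answer, with the round trip as the intended quantity.
- Emission factor: per unit of distance, from public data; source and unit not given.
- Share *q* of the emission-weighted distance that is answered one way: **not in the documents**. The values below are assumptions.
- 1 mile = 1.609 km.

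**Formula.** The calculation implied by sections 2 and 5d is

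avoided emissions = 18 × round-trip distance × emission factor.

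**One participant.** A one-way answer used as a round trip gives 18 × (distance ÷ 2) × factor, which is 0.5 of the true value. A correct round-trip answer that the analyst doubles gives 2.0 times the true value.

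**Study total.** If answers are used as round trips, result ÷ truth = (1 − *q*) × 1 + *q* × 0.5 = 1 − *q*/2. If answers are doubled, result ÷ truth = (1 − *q*) × 2 + *q* × 1 = 2 − *q*.

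| Assumed *q* | Used as round trips | Doubled by the analyst |
|---|---|---|
| 0% | 1.00 | 2.00 |
| 10% | 0.95 | 1.90 |
| 25% | 0.875 | 1.75 |
| 50% | 0.75 | 1.50 |
| 100% | 0.50 | 1.00 |

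Used as the prompt intends, the total is understated by 5% at *q* = 10%, by 12.5% at 25% and by 25% at 50%. The twofold limit is reached only if every answer is one way, or if every answer is a round trip and all are doubled.

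**Unit.** Kilometres read as miles multiply a value by 1.609. Miles read as kilometres multiply it by 1 ÷ 1.609 = 0.621.

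**Both faults in the same direction.** The limits are 2 × 1.609 = 3.22 and 0.5 × 0.621 = 0.31, and only if every answer is affected by both.

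**The case against.** The strongest reply is that the instruction a participant acts on is clear. Elsewhere in Appendix 3 the left-hand cell often serves as a topic and the right-hand cell says what to write. Here the right-hand cell spells out both legs of the journey. That stands: the intended quantity is a round trip, and label and prompt are not two equal requests. Most participants may well comply.

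It is also fair that no misreading rate is documented, and that doubling would require the analyst to disregard the study's own prompt. Kilometre answers are less likely at a UK hospital where the only travel unit in the protocol is miles: section 7 has "fuel costs paid at 45p per mile for study visits". That rate is not linked to the Appendix 3 item, however, and the measurement visits are at the University of Bath, so mileage claims for them describe a different journey.

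A reader might infer that the recorded distances would be beyond repair. The documents do not support that. Participants attend in person in weeks 0 and 7, and an unclear answer can be queried at either visit. What remains is that no section provides for such a check, and a plausible one-way figure would not look unclear.

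Lastly, the outcome is a hypothetical comparison built on a self-reported best estimate and described in a largely descriptive analysis. This limits the importance of the point, but a known, avoidable inconsistency is still worth removing.

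**Conclusion.** The inconsistency is real but minor. The label reads as one way, the prompt asks for a round trip, and no unit is printed. A participant who answers the label halves their own contribution to the avoided-emissions estimate.

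A reader might infer that the environmental result as a whole is likely to be wrong by a factor of two. The documents do not support that: the prompt states the round trip, and nothing says that answers will be doubled. Nor is two the outer limit once the missing unit is counted, since the combined extreme is about 3.2. Neither extreme is an expected error. The 5% to 25% understatement rests on the assumption that 10% to 50% of the emission-weighted distance is answered one way and that answers are otherwise used as the prompt intends. The true share cannot be known from the documents.

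The progression criteria use adherence and retention only (section 5a), and the sample size is built on them, so neither is affected.

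**What to change.** 1. In Appendix 3, reword the label to match the prompt and print the unit, for example: *Round-trip distance, home to RUH and back, in miles*.
2. Have the researcher check the answer with the participant at the week 0 visit. For any form already completed, confirm direction and unit at the week 7 visit.
3. In section 5e, state that avoided emissions = 18 × recorded round-trip distance × emission factor, that the recorded distance is not doubled, and that the emission factor is expressed in the same distance unit.

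The cost is one line on a form, one or two sentences in section 5e and a brief check at a visit that already takes place. Participants are asked for nothing new. Changing to a one-way question and doubling the answer would work equally well, but aligning the label with the existing prompt is the smaller change.
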